Table 17.6:	Dose Adjustments for INR Elevation	139
Table 17.7:	Estimated Glomerular Filtration Rate Based on Age	140

LIST OF FIGURES

Figure 3.1: DU176b-C-U313 Overall Study Design			
Figure 17.1:	Blood Pressure Levels for Boys by Age and Height Percentile	141	
Figure 17.2:	Blood Pressure Levels for Girls by Age and Height Percentile	143	
Figure 17.3:	Growth Chart (Boys 2 to 20 Years of Age)	145	
Figure 17.4:	Growth Chart (Girls 2 to 20 Years of Age)	146	
Figure 17.5:	Growth Chart (Boys Birth to 24 Months of Age)	147	
Figure 17.6:	Growth Chart (Girls Birth to 24 Months of Age)	148	

LIST OF ABBREVIATIONS

ABBREVIATION	DEFINITION		
AE	adverse event		
ALP	alkaline phosphatase		
ALT	alanine transaminase		
ANA	antinuclear antibody		
aPTT	activated partial thromboplastin time		
AST	aspartate transaminase		
ATE	arterial thromboembolism		
BMI	body mass index		
BP	blood pressure		
CEC	Clinical Events Committee		
CFR	Code of Federal Regulations		
CHD	congenital heart disease		
CI	confidence interval		
CMV	cytomegalovirus		
CRF	case report form		
CRNM	clinically relevant non-major		
CRO	Contract Research Organization		
СТ	computed tomography		
CVL	central venous line		
DVT	deep vein thrombosis		
EBV	Epstein-Barr virus		
EC	Ethics Committee		
eCRF	electronic case report form		
EDC	electronic data capture		
eGFR	estimated glomerular filtration rate		
EIU	exposure in utero		
FXa	activated Factor X		
GCP	Good Clinical Practice		
ICF	informed consent form		
ABBREVIATION	DEFINITION		
--------------	---	--	--
ICH	International Council for Harmonisation		
IDMC	Independent Data Monitoring Committee		
INN	international non-proprietary name		
INR	international normalized ratio		
IRB	Institutional Review Board		
ISTH	International Society on Thrombosis and Haemostasis		
IV	intravenous		
IXRS	Interactive Web/Voice Response System		
LFT	liver function test		
LMWH	low molecular weight heparin		
LOA	List of Abbreviations		
MI	myocardial infarction		
mITT	modified intention-to-treat		
MRI	magnetic resonance imaging		
MRV	magnetic resonance imaging with venography		
NSAID	non-steroidal anti-inflammatory drug		
NVAF	nonvalvular atrial fibrillation		
PCC	prothrombin complex concentrate		
PD	pharmacodynamic		
PE	pulmonary embolism		
P-gp	P-glycoprotein		
РК	pharmacokinetic		
PT	prothrombin time		
QD	once a day		
QOL	quality of life		
RBC	red blood cell		
SAE	serious adverse event		
SAP	statistical analysis plan		
SC	subcutaneous		
SD	standard deviation		

ABBREVIATION	DEFINITION		
SEE	systemic embolic event		
SOC	standard of care		
SOP	standard operating procedures		
SUSAR	suspected unexpected serious adverse reaction		
TBL	total bilirubin		
ТЕ	thromboembolic event		
TEAE	treatment-emergent adverse event		
UFH	unfractionated heparin		
ULN	upper limit of normal		
US	ultrasonography		
VKA	vitamin K antagonist		
VTE	venous thromboembolism		
WBC	white blood cell		

1. INTRODUCTION

1.1. Background

Children with cardiac diseases, including cardiomyopathy and congenital heart disease (CHD) constitute a major proportion of children seen in tertiary hospitals with thromboembolic disease. In addition, more than 80% of the children receiving primary anticoagulant prophylaxis are being treated for complex CHD or severe acquired cardiac illnesses.

In children with cardiac disease, thromboembolic disease develops as a result of altered hemodynamics, prosthetic materials, surgically damaged blood vessels, intravenous (IV) catheters, and cardiopulmonary bypass. To prevent this potential life-threatening complication, some categories of pediatric cardiac patients, including patients with Fontan circulation, severe cardiomyopathy, and mechanic heart valve prostheses, are treated with vitamin K antagonists (VKAs) or heparin.

Many children with CHD require long-term thromboprophylaxis to decrease the morbidity and mortality secondary to the thromboembolic phenomenon. The advances in medical and cardiosurgical techniques have led to improved survival in children with CHD; thus, the overall use of anticoagulation has increased. The overall incidence of thrombotic complications in patients undergoing cardiac surgery for CHD remains difficult to evaluate due to a lack of data. Giglia et al² showed an incidence of clinically evident TE of 3.6% of 1930 total cardiac operations performed. More recently, Manlhiot et al³ revealed that 11% of cardiac operations over a 39-month period were complicated by TEs.

1.2. Study Rationale

Currently available anticoagulants have significant limitations especially in the pediatric population. At the moment, the commonly used agents for long-term anticoagulation in children are low molecular weight heparin (LMWH) and VKAs. The important disadvantages of LMWH (such as enoxaparin) are subcutaneous (SC) administration, thrombocytopenia, and therapeutic level management. Vitamin K antagonists (such as the coumarins: warfarin, acenocoumarol, or phenprocoumon) are indirect coagulation inhibitors, which act by blocking the vitamin K dependent liver synthesis of the plasma coagulation factors II, VII, IX, and X. These agents have been the only oral anticoagulants available for the last 50 years. The use of VKAs is complicated by several inherent problems including a delayed onset of antithrombotic action, a narrow therapeutic index that requires close laboratory monitoring using the international normalized ratio (INR), an unpredictable and variable pharmacological response, and food and drug interactions requiring frequent dosage adjustment. Monagle et al showed that 41% of all warfarin measurements were below the target range, which is not uncommon in children taking warfarin⁴. Therefore, there exists a need for a safe, effective, and more easily managed oral antithrombotic agent for the treatment of pediatric subjects with thromboembolic disease.

Edoxaban is an oral direct inhibitor of activated Factor X with predictable pharmacokinetics and pharmacodynamics. As a result, anticoagulant effects are more likely to remain within the therapeutic range, thereby decreasing the likelihood of bleeding, and potentially removing the need for dose adjustment or frequent monitoring. These advantages may result in increased patient satisfaction and adherence compared with existing anticoagulants.

In 2015, edoxaban was approved for the following indications in the United States:

- To reduce the risk of stroke and systemic embolism in subjects with nonvalvular atrial fibrillation (NVAF) with limitation of use in patients with creatinine clearance (CrCl) >95 mL/min.
- Treatment of deep vein thrombosis (DVT) and pulmonary embolism (PE) following 5 to 10 days of initial therapy with a parenteral anticoagulant.

In the European Economic Area and Japan, edoxaban was approved in 2015 for the following indications:

- Prevention of stroke and systemic embolism in adult subjects with NVAF with one or more risk factors, such as congestive heart failure, hypertension, age ≥75 years, diabetes mellitus, prior stroke or transient ischemic attack with no limitation of use.
- Treatment of DVT and PE, and prevention of recurrent DVT and PE in adults.

As of 21 Oct 2018, edoxaban is authorised in 45 countries and is marketed in 30 countries worldwide.

This study will compare the safety of edoxaban with the standard of care (SOC) treatment in pediatric subjects with cardiac disease who need anticoagulation to prevent primary and secondary thromboembolic disease. Further data on edoxaban development are provided in the most recent Investigator's Brochure⁵.

1.3. Risk/Benefit

Although pediatric subjects are at less risk than adults for the development of thromboembolic event (TE), embolic disease remains an uncommon condition, but it does occur and is well described in children and adolescents with or without risk factors. Thrombosis is an increasingly recognized complication occurring primarily in children with serious underlying conditions and most often associated with IV catheters,⁶ and is also recognized in neonatal and pediatric practice due to more sophisticated diagnostic tools being available. In children with cardiac disease, thromboembolic disease develops as a result of altered hemodynamics, prosthetic materials, surgically damaged blood vessels, intravenous catheters, and cardiopulmonary bypass. To prevent this potential life-threatening complication, some categories of pediatric cardiac patients, including patients with heart failure, Fontan circulation, severe cardiomyopathy (Kawasaki disease), and mechanic heart valve prostheses, are treated with less advanced therapy such as VKAs or heparin which requires intensive therapeutic monitoring.

Many children with CHD require long-term thromboprophylaxis to decrease the morbidity and mortality secondary to the thromboembolic phenomenon. The advances in medical and cardiosurgical techniques have led to improved survival in children with CHD; thus, the overall use of anticoagulation has increased. The overall incidence of thrombotic complications in patients undergoing cardiac surgery for CHD remains difficult to evaluate due to a lack of data. Giglia et al² showed an incidence of clinically evident TE of 3.6% of 1930 total cardiac operations performed. More recently, Manlhiot et al³ revealed that 11% of cardiac operations over a 39-month period were complicated by TEs. Symptomatic thrombotic manifestation is recorded in 0.07/10,000 children,

5.3/10,000 admissions of children and 24/10,000 admissions of newborns to intensive care units.^{1,7,8} According to the U.K. registry (British Pediatric Surveillance Unit), the estimated incidence of thromboembolic events was 0.07/10,000 children (excluding stroke), with 89% having venous involvement⁷. Besides the greater awareness, an objective increase in childhood thrombosis is attributed to medical advances in the treatment of critically ill patients. This seemingly contradictory observation is readily explained by the increasing use of central catheterization and innovative interventional procedures in the treatment of premature infants, neonates and older children who are critically ill, suffering from complex cardiac defects, and from malignant disease, respectively.

Safety and effectiveness of edoxaban development is an ongoing program with 2 Phase 3 studies in the pediatric population (venous thromboembolism [VTE-U312 study] and arterial thromboembolism [ATE-U313 study]). In principle, based on current adult data obtained on edoxaban, edoxaban is also considered to be suitable for the pediatric population and supported by the FDA and EMA request for pediatric studies in select populations.

The DU176b-A-U157 study (currently ongoing in the US, Canada, and Rest of the World [ROW]) will evaluate and establish the pharmacokinetics (PK), the pharmacodynamics (PD), the safety and tolerability of edoxaban in pediatric patients following single-dose oral administration. It will also evaluate the palatability of the liquid oral suspension of edoxaban. Pediatric patients who are at risk of thromboembolic events and may need anticoagulation are eligible for inclusion in the study. The goal of this study is to identify pediatric doses that are age appropriate and provides comparable exposure to adult efficacious doses to guide dose selection for the Phase 3 studies in a pediatric population who have confirmed VTE (U312 study) or patients with cardiac disease at risk of thromboembolic events (U313 Study) which require anticoagulant therapy.

The dose for 3 of the 5 age cohorts 12 to <18, 6 to <12, and 2 to <6 years has been defined from the U157 study, and age cohort enrollment in the U312 VTE study and U313 will be sequential based on the availability of data derived from U157. Note: doses for age cohorts 6 months to <2, and 38 weeks gestation to <6 months) need to be defined. No safety concerns related to study drug have been observed in these subjects. In addition, approximately 135 subjects (12 to <18 years) and 35 subjects (6 to <12 years) as of April 2019 in the Phase 3 U312 VTE study have been enrolled without clinical sequelae as reviewed by the Independent Data Monitoring Committee (IDMC).

There are potential benefits for trial participation as well as receipt of the study drugs in this open label design, as patient compliance and lifestyle will be improved by taking an oral medication compared to an injectable (enoxaparin) or and VKA which has therapeutic monitoring requirements and potential food interactions. Indirect benefits to the patients enrolled in this trial are the free medical tests received at screening and during the study. The data derived from this study could potentially benefit pediatric patients when the study data is disclosed and becomes publically available or lead to a possible update of the edoxaban drug label for pediatric use.

The safety monitoring practices employed by this protocol, DU176b-C-U313, (ie, physical examinations, vital signs, AEs, clinical laboratory and coagulation assessments, and urinalysis)

are considered adequate to protect the patients' safety. The IDMC can recommend termination of the study based on concern about significantly higher bleeding risk relative to one of the study arms, concern about drug-induced liver injury or any other safety concern based on benefit/risk evaluation. Therefore, any risk associated with participation in this trial is fully evaluated during the course of the trial by an IDMC to ensure patient risk is minimized.

In conclusion, for the individual pediatric patient, any benefit associated with participation in this trial is based on the confirmed efficacy and safety profile of edoxaban compared to SOC in the adult population from large Phase 3 studies, and the predicted benefit for the overall pediatric population. Any risk is minimized, as the trial is an open label design, is highly monitored by an IDMC and associated risks controlled and evaluated for the individual patient. Indirect benefits to the patients enrolled in this study are the free medical tests received at screening and during the study. However, the data derived from this study could potentially benefit pediatric patients if it leads to an extension of the edoxaban label. This research may give rise to new or better drug treatments for this vulnerable patient population. The information from this study may benefit other pediatric patients in the future.

2. STUDY OBJECTIVES, HYPOTHESIS AND ENDPOINTS

2.1. Study Objectives

2.1.1. Primary Objectives

The primary objective is to compare the safety of edoxaban with the SOC in pediatric subjects with cardiac diseases at risk of thromboembolic complications who need primary or secondary anticoagulant prophylaxis with regard to the combination of major and clinically relevant non-major (CRNM) bleedings per International Society on Thrombosis and Haemostasis [ISTH] definition¹ occurring in the Main Treatment Period: from the date of first dose of study drug to Month 3 Visit, or to the date of last dose of study drug plus 3 days if study treatment is discontinued, whichever is earlier.

2.1.2. Secondary Objectives

2.1.2.1. Key Secondary Objectives

The key secondary objectives are:

- To compare the efficacy of edoxaban against SOC with regard to the development of symptomatic thromboembolic events (TE) in the systemic arterial or venous pathways including deep vein thrombosis (DVT), pulmonary embolism (PE), stroke, intracardiac thrombus, systemic embolic event (SEE), myocardial infarction (MI), and asymptomatic intracardiac thrombus identified by cardiac imaging occurring from randomization to Month 3 Visit.
- To compare the safety of edoxaban against SOC with regard to all bleedings which occur in the Main Treatment Period: from the date of first dose of study drug to Month 3 Visit, or to the date of last dose of study drug plus 3 days if study treatment is discontinued, whichever is earlier.
- To compare the efficacy of edoxaban against SOC with regard to death as a result of a TE occurring from randomization to Month 3 Visit
- To compare edoxaban against SOC with regard to all-cause mortality from randomization to Month 3 Visit.
- To assess the safety of edoxaban with regard to the combination of major and CRNM bleedings occurring during the Extension Period (from Month 3 Visit to last dose plus 30 days).
- To assess the efficacy of edoxaban with regard to the development of symptomatic TE or asymptomatic intracardiac thrombus identified by cardiac imaging occurring during the Extension Period.
- To assess the safety of edoxaban with regard to all bleedings occurring during the Extension Period.
- To assess the efficacy of edoxaban with regard to death as a result of a TE occurring during the Extension Period.

- To assess the efficacy of edoxaban with regard to all-cause mortality occurring during the Extension Period.
- To evaluate the population pharmacokinetics and pharmacodynamics of edoxaban in relation to the efficacy and safety endpoints in subjects with cardiac conditions at risk of TE.

2.1.2.2. Other Secondary Objectives

Not applicable.

2.1.3. Exploratory Objectives

The exploratory objectives are:

- To assess the quality of life (QOL) using validated questionnaires.
- To compare the intra-patient safety (Investigator reported bleeding) and efficacy (Investigator reported TE) during the Main Treatment Period compared with the prior treatment occurring within 3 months of randomization.
- To compare edoxaban regimen with available existing historical data based on literature review and search for registered clinical trials with similar endpoints.
- To analyze the primary prevention and secondary prevention of TE.

2.2. Study Hypothesis

This study is designed to assess the hypothesis that the administration of edoxaban will be at least as safe as the current SOC (unfractionated heparin [UFH] or LMWH and/or VKA) with regard to the combination of major and CRNM bleedings after 3 months of therapy in pediatric subjects with cardiac disease at risk of thromboembolic events.

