5. STUDY TREATMENT(S)

5.1. Assigning Subjects to Treatments and Blinding

5.1.1. Treatment Groups

All subjects will be assessed for eligibility in the study in accordance with the inclusion/exclusion criteria. Eligible subjects will be stratified and randomized as follows:

• All eligible subjects will be stratified by:

Type of underlying heart disease:

Kawasaki disease

Fontan surgery

Heart failure (HF)

Others (which can include post-surgical procedures for congenital heart disease other than Fontan surgery)

Subjects with underlying disease other than Kawasaki will be further stratified by concomitant use of low dose aspirin (1 to 5 mg/kg/day).

• Randomized in a 2:1 ratio (edoxaban:SOC, respectively) into 1 of 2 treatment arms:

Edoxaban-treatment arm: subjects will receive a selected dose of edoxaban

OR

SOC-treatment arm: subjects will receive SOC anticoagulant according to clinical site's SOC treatment, as follows (alone or in combination):

Heparin, including UFH or LMWH

Vitamin K antagonist (VKA) with potential bridging with heparin based therapy until VKA INR is in therapeutic range

After Month 3, all subjects who continue in the Extension Period and are on SOC will be offered edoxaban treatment and dosed according to their cohort age at the time of subject consent. During the extension period of the study, check the body weight prior to dosing and adjust dosage accordingly. Frequency of dosage changing is up to the Investigator's discretion.

Subjects from 1 to <18 years of age will be enrolled in the study as soon as the dosing regimen is established for each age cohort in the Phase 1 single-dose U157 study.

Additionally, subjects less than 1 year of age will be admitted to the study after review by the IDMC of safety data of 50% of subjects in the 1 to <18 years of age group who have completed the Main Treatment Period of 3 months (50 subjects in edoxaban arm and 25 subjects in SOC arm).

Subjects younger than 6 years of age will only receive edoxaban granules for oral suspension, which will give more flexibility to adjust mg/kg dose. Doses for all age groups will be selected to elicit target exposures comparable to those achieved from the adult Phase 3 study of 60 mg.

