11. STATISTICAL METHODS

11.1. General Statistical Considerations

All efficacy analyses will be based on the modified intention-to-treat (mITT) Analysis Set and will be performed based on the treatment group assigned at randomization.

Safety analysis will be performed using the Safety Analysis Set. Subjects will be analyzed according to actual treatment received.

All analyses for the Extension Period will be based on subjects who participate in the Extension Period and take only edoxaban in the Extension Period, in the specified analysis set, and will be summarized for the edoxaban treatment group. Data listings will be prepared for subjects who are randomized to the SOC arm, participate in the Extension Period, and do not switch to edoxaban right after the Month 3 Visit.

All confidence intervals will be descriptive and will be two-sided 95% confidence interval (CI), unless otherwise specified.

Unless otherwise specified, the baseline value of an efficacy variable for a subject is the last nonmissing measurement before the randomization, and the baseline value of a safety variable is the last non-missing measurement before the first dose of the study drug.

In general, missing data will not be imputed for the purpose of data analysis. No visit windows will be used for analysis.

Continuous variables will be summarized by the number of observations, mean, standard deviation, median, and minimum and maximum values. Categorical variables will be summarized using frequency counts and percentages. Summary statistics will be presented by treatment group.

There is no formal statistical interim analysis planned. However, after the first 50 subjects enrolled in the edoxaban treatment group and 25 subjects enrolled in the SOC treatment group complete the first 3-month treatment period, an interim assessments by IDMC of safety endpoints will be performed to allow for enrollment of subjects <1 year of age into study.

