11.4.3. Safety Analysis

11.4.3.1. Analysis of Bleeding Events

The primary safety endpoint is the composite of major and CRNM bleeding events that occur during the Main Treatment Period: from the date of first dose of study drug to the Month 3 Visit, or to the date of last dose of study drug plus 3 days if study treatment is discontinued, whichever is earlier. This analysis will be based on CEC adjudication results.

The time to major or CRNM bleeding occurring during the Main Treatment Period will be compared between treatment groups for subjects in the Safety Analysis Set, using the Cox proportional hazards regression model with treatment group, concomitant usage of aspirin at baseline, and underlying disease (Kawasaki disease, Fontan surgery, heart failure or Other) as covariates. Hazard ratio between edoxaban and SOC treatment group will be calculated with corresponding 95% CI. The incidence, annualized event rate, and rate difference between edoxaban and SOC treatment groups will also be calculated.

In addition, incidence, annualized event rate and rate difference between edoxaban and SOC treatment groups with corresponding 95% CI will be calculated for following endpoints for Safety Analysis Set for the Main Treatment Period. Incidence and annualized event rate will also be calculated for the following endpoints occurring from the day after Month 3 Visit to date of last dose of study drug plus 30 days in the Extension Period.

- Major and CRNM bleeding event combined
- Major bleeding event
- All bleeding event (major, CRNM, and minor bleeding combined)

The above 3 categories of bleeding endpoints will also be summarized for the periods and subjects below:
- Incidence, annualized event rate, and rate difference will be calculated for events occurring from the date of first dose of study drug to the date of last dose of study drug plus 30 days for subjects who do not participate in the Extension Period.
- Incidence and annualized event rate will be calculated for events occurring from the day after Month 3 Visit to the data of last dose of study drug for subjects who participate in the Extension Period.

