11.6. Sample Size Determination

A sample size of 150 subjects was chosen for this study. This study is not a powered study intended to draw conclusions based on statistically significant differences between edoxaban and SOC. An adequately powered study would be unachievable due to the significantly large sample size required and the enormous challenge to enroll these pediatric patients. Although the sample size is not based on statistical consideration, assuming major and CRNM bleeding event rates (which are the primary endpoints for this study) are the same as observed in adult Hokusai-VTE Study, (ie, 8.5% and 10.3% in edoxaban and SOC arms, respectively); with 100 subjects in edoxaban arm and 50 subjects in standard of care arm, the 95% CI around the point estimate of the risk difference between edoxaban and SOC is -11.8%, 8.2%..

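### Section 2.2 says the study is designed to assess that edoxaban is at least as safe as SOC, but the plan has no margin or decision rule and only about 14 expected bleeding events

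*Combined protocol and SAP*

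**What the plan says.** Section 2.2 sets the hypothesis: "This study is designed to assess the hypothesis that the administration of edoxaban will be at least as safe as the current SOC", for the composite of major and CRNM bleeding after three months of therapy.

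The other statistical text is more modest:

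- Section 11.1: "All confidence intervals will be descriptive and will be two-sided 95% confidence interval (CI), unless otherwise specified".
- The synopsis, under the primary safety endpoint, also calls the analysis descriptive.
- Section 11.6: "This study is not a powered study intended to draw conclusions based on statistically significant differences between edoxaban and SOC". It adds that the 150 subjects were not derived statistically and that an adequately powered trial could not be achieved.
- Section 11.6 illustrates precision on the risk-difference scale only, with a 95% CI of -11.8% to 8.2%. It assumes rates from an adult VTE study.
- Section 11.4.3.1 compares time to first major or CRNM bleed "using the Cox proportional hazards regression model with treatment group, concomitant usage of aspirin at baseline, and underlying disease". It continues: "Hazard ratio between edoxaban and SOC treatment group will be calculated with corresponding 95% CI". The same section also plans incidence, annualized event rate and a rate difference with 95% CI for this composite.

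No non-inferiority margin, test or decision rule appears in the text supplied. Section 11.7 leaves methods detail to the SAP.

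**The concern.** An at-least-as-safe hypothesis is of non-inferiority type. To be assessed, it needs a statement of how much excess bleeding would still count as acceptable, and an interval narrow enough to be compared with that amount. The plan supplies neither, so Section 2.2 credits the design with a property it lacks.

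The disclaimer in Section 11.6 does not close the gap. It rules out conclusions that rest on statistically significant differences, but an at-least-as-safe reading needs no significant difference. The result that invites it is a hazard ratio near 1 with an interval spanning 1, which is a likely outcome with so few events. With Section 2.2 as worded, such a result could be presented as support for the stated hypothesis. Section 1.3 foresees that the data may contribute to pediatric labelling, so the distinction between no difference shown and no harm shown matters.

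**Working it through.** **Inputs**

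- Event rates (Section 11.6): "8.5% and 10.3% in edoxaban and SOC arms, respectively".
- Arm sizes (Section 11.6): "with 100 subjects in edoxaban arm and 50 subjects in standard of care arm", in line with the 2:1 allocation of Section 5.1.1.
- Two-sided 95% intervals (Section 11.1).
- No dropout rate is stated, and none is applied.

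**1. The plan's own figure, reproduced**

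Risk difference = 0.085 - 0.103 = -0.018.

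SE = sqrt(0.085 × 0.915/100 + 0.103 × 0.897/50) = 0.0512.

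95% CI = -0.018 ± 1.96 × 0.0512 = -11.84% to 8.24%. This matches Section 11.6, so the stated interval is arithmetically right.

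**2. The same assumptions on the hazard ratio scale**

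Expected events = 100 × 0.085 + 50 × 0.103 = 8.5 + 5.15 = 13.65.

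HR under proportional hazards = ln(1 - 0.085)/ln(1 - 0.103) = 0.817.

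SE(log HR) ≈ sqrt(1/8.5 + 1/5.15) = 0.558.

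95% CI = 0.817 × exp(±1.96 × 0.558) = 0.274 to 2.442.

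The interval runs from a hazard about 73% lower to one about 2.4 times higher.

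Other approximations barely move it:

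| Approximation | 95% CI |
|---|---|
| Schoenfeld variance with 2:1 allocation | 0.265 to 2.518 |
| Ratio of proportions (0.825) used as the HR | 0.276 to 2.465 |
| 8 and 5 whole events | 0.262 to 2.445 |
| 9 and 5 whole events | 0.302 to 2.685 |

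**3. How often would the upper limit fall below a given bound?**

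The documents give no margin, so every bound m here is an assumption, shown over a range.

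P(upper limit < m) = Φ[(ln m - ln 0.817)/0.558 - 1.96]

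| Assumed bound m | Chance at the planning rates |
|---|---|
| 1.25 | 12% |
| 1.5 | 19% |
| 2.0 | 36% |
| 2.5 | 52% |
| 3.0 | 64% |

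If both arms had the 10.3% rate (true HR 1), events are 10.3 + 5.15 = 15.45 and the SE is sqrt(1/10.3 + 1/5.15) = 0.540. The chance is then about 11% for m = 1.5 (Φ[0.405/0.540 - 1.96]) and 25% for m = 2.0 (Φ[0.693/0.540 - 1.96]).

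**4. Sensitivity to the adult rates**

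Hold the HR at 0.817 and assume that only a fraction f of these events occurs. The SE becomes 0.558/sqrt(f).

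- f = 0.75: about 0.23 to 2.89.
- f = 0.5: about 0.17 to 3.84.

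Step 2 is also unadjusted and assumes full follow-up. The planned Cox model carries four covariate parameters besides treatment (one for aspirin, three for the four-level disease factor) on about 14 events. Follow-up is cut at last dose plus 3 days when treatment stops. Both would tend to widen the actual interval.

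**The case against.** The strongest reply is that the plan already discloses its limits. Section 11.6 says the study is unpowered and why, Section 11.1 makes the intervals descriptive, and the synopsis calls the primary analysis descriptive. No test or alpha turns Section 2.2 into a formal claim, and nowhere does the plan propose to declare safety from a wide interval. This stands, and it confines the point to a mismatch of wording.

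It also stands that the precision in Section 11.6 is not detached from the analysis. Section 11.4.3.1 plans a rate difference alongside the hazard ratio. The stated upper limit already shows the imprecision: 10.3% + 8.2% = 18.5%, or 18.5/10.3 = 1.8 times the SOC rate. The missing hazard ratio interval alone would be only a missing detail.

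Stronger readings are tempting but not supported:

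- A reader might infer that the design cannot exclude a doubling of bleeding. It can: the chance is about 36% at the planning rates and 25% at equal rates. Unlikely to exclude is as far as the figures go, and the bound of 2.0 is itself an assumption.
- A reader might infer that Section 11.6 disclaims all conclusions. It disclaims only those based on statistically significant differences.
- A reader might infer that the trial is too small and must grow. Section 11.6 explains why a powered trial is not feasible, and nothing here contradicts that.

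What the reply does not answer is that disclaiming significance-based conclusions leaves the at-least-as-safe reading open, because that reading rests on not finding a difference.

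**Conclusion.** The point holds as a conflict between the stated hypothesis and the design. Section 2.2 says the study is designed to assess something for which it has no margin, no decision rule and, on its own planning figures, little precision: about 14 events and an unadjusted hazard ratio CI of about 0.27 to 2.44. The plan's risk-difference interval is correct, and its lack of power is openly stated.

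The size rests on adult rates that Section 11.6 offers only as an illustration, on full follow-up and on no covariate adjustment. Fewer events in children would widen the interval. The 19% and 36% chances depend on assumed bounds of 1.5 and 2.0. How the results will be reported is not known; the concern is what the current wording permits. The change should be made because it settles what the trial may conclude, although it alters no analysis.

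**What to change.** Replace the hypothesis in Section 2.2 with an estimation statement consistent with Sections 11.1 and 11.6, for example:

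*The study will estimate the hazard ratio and the rate difference for major/CRNM bleeding between edoxaban and SOC with descriptive 95% CIs; it is not designed to conclude that edoxaban is at least as safe as SOC.*

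Optionally add to Section 11.6:

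*At these rates about 14 events are expected and the approximate unadjusted 95% CI for the hazard ratio, assuming no dropout, would be 0.27 to 2.44; the covariate-adjusted interval may be wider.*

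The cost is one or two sentences in an amendment. Sample size, endpoint, data collection and analysis do not change. The downside is that the stated aim and the planning precision look less favourable.
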